Our hypothesis is that this nurse-led, evidence-based, coordinated care management intervention will achieve: (a) higher adherence to PD quality indicators, and (b) better patient outcomes of health-related quality of life, patient self-efficacy and perceptions of care quality, relative to usual care over 18 months. To accomplish Specific Aim #1, veterans with PD will be recruited from Greater Los Angeles (GLA), Las Vegas, Loma Linda, Long Beach and San Diego Healthcare Systems, to achieve a target number of 300 enrolled and randomized in a 1:1 ratio to receive either the CHAPS care intervention, or care as usual (300 participants will be randomized equally into control and intervention groups, i.e. 150 in each group). Process measures and patient outcome data will be collected via structured telephone interviews with patients at baseline, 6, 12, and 18 months, and via abstraction of medical records. The first 204 participants will receive a 24-month survey to adjust for a 6-month delay in the project.

Specific Aim #2 is to (a) examine the extent of the nurse-led PD care management intervention implementation and factors associated with variations in degree of implementation, and (b) measure associated costs and cost offsets from the VA perspective, to provide regional and national VA leadership with data to guide decisions about the value of sustaining this PD care management intervention, and about feasibility of further dissemination within VA, if shown to be effective.

The hypothesis is that a process evaluation and a cost analysis will demonstrate that the intervention is feasible to implement and to sustain in terms of resource utilization. To achieve Specific Aim 2, three data collection methods will be used: (a) abstraction of data from: minutes of project meetings and staff satisfaction questionnaires of key staff including care managers and clinician champions on clinician position/role/responsibilities and impressions of and experiences with CHAPS, including suggestions for improvement, use of information systems, use of practice guidelines and templates, and

[figure not shown]

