communication/coordination between and within organizations, (b) analysis of interview data with a randomly selected subset of study participants in the intervention arm (collected after the study follow-up period ends; at 18 month survey interview or 24 month for the first 204 enrollees); and (c) a cost assessment of the intervention (intervention program costs; cost offset of healthcare utilization for intervention arm relative to usual care), using data from VISN Data Warehouse, from the VA perspective.

Because of this research team's considerable experience in PD health services research, and previous care management implementation studies in dementia care; and championed by local and national VA and PD-advocacy groups; this team is well-positioned to conduct this randomized controlled trial (RCT) of a PD care management intervention. Study results will be used to inform future research including a larger RCT in multiple geographical locations, and policy decisions regarding care model adoption by the VA for future spread, both of which can be facilitated via the six VA Parkinson's Disease Research, Education, and Clinical Center (PADRECC) national network and the "National VA Parkinson's Disease Consortium."

BACKGROUND

Background – 1. Scientific Rationale. The care management intervention we plan to implement and test in this randomized controlled trial has been developed based on the Chronic Care Model (CCM).²⁻⁴ The advantage of using this well-established model is that it focuses on multiple structural components of care that need to be in place to foster higher rates of evidence-based care processes, which in turn should achieve optimal health for individuals with chronic illnesses. The six CCM-components are illustrated in Figure 1 below and are (1) the health system, (2) community engagement and resources, (3) delivery system re-design, (4) self-management support, (5) decision support, and (6) clinical information systems. A central feature of the model we have developed is a *nurse care manager*, who will lead the execution and coordination of the care management activities to be carried out with veterans having PD.

Figure 1. Wagner's Chronic Care Model Used to Guide the VA PD Intervention Design

Delivery System Re-design: Rationale for Nurse Care Managers Using Tools, Protocols, and Algorithms to Provide Coordinated PD Care.

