Background 2 - Study Context and Implications. This study will be conducted in VISN 22 medical centers in the Southwest United States that are part of an existing regional network of Parkinson's Disease Research, Education, and Clinical Center (PADRECC) sites. Network sites have a clinical champion and regular movement disorder clinics, ongoing journal clubs by teleconference, and referral and research collaborations across the eight sites in two VISNs covering southern California, southern Nevada, Arizona, and New Mexico. However, this care model has been physician visit-based, and there are not enough movement disorder specialists to manage all veterans with PD seen in this region of the US. The new model we have developed will overlay the existing care delivery structure. In addition, it will meet the objectives originally envisioned for

the PADRECCs, to develop new clinical care models for PD and seek research funding to rigorously evaluate their impact on quality and outcomes.

Background 3 - Study features that will enable success in addressing problem of gaps in VA PD care.

To our knowledge, there has never been a trial of a coordinated care delivery program for Parkinson's disease care, either within or outside of VA. Thus, a randomized trial of this carefully-designed, coordinated care management intervention will provide new knowledge not only about efficacy of this scientifically-grounded intervention, but also the feasibility of its widespread application, by measuring cost and by documenting contextual factors about its implementation. The study builds on previous research by our group including [name] pilot study, and is based on an established model of chronic disease management that incorporates the collaborative efforts of the VA and the PD advocacy groups in a region, and which has support from administrative leadership at participating facilities and PADRECC clinical champions. It is adequately powered, and the 18-month follow-up should provide a sufficient timeframe to execute care management activities that can produce improvements in process measures in PD care and their translation into improved health outcomes.

SIGNIFICANCE

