Veteran survey: telephone interview (Appendix 6). Telephone surveys will be administered to all study participants by trained research assistants. A baseline interview of about 30-40 minutes duration will be administered prior to randomization. Three follow-up telephone interviews will also be about 30-40 minutes duration. Each will be administered at 6, 12, and 18 months (and 24 months for the first 204 enrollees) after enrollment by a research assistant who will be blinded to randomization status. Procedures to promote retention will include allowing the interviews to be broken into multiple sessions, and scheduling at times that are convenient for the veteran. Study participants will be provided \$25 per survey as recognition for their time. SSNs will be obtained from CPRS to process subject payment. SSNs will be included in the Patient Registry which will be stored in an Excel file, and will be placed in a password protected file on a VA desktop computer that is backed-up on the secure server at the VA Sepulveda HSR&D COE. Occasionally Veterans move and/or change their telephone numbers. In the event the study RA is unable to reach an enrolled participant by telephone in order to administer the Evaluation survey (s), an “Unable to Reach for Survey Letter” (Appendix 17) will be mailed to the enrolled participant. The letter aims to offer a participant the opportunity to continue with the study and to complete the Evaluation surveys at baseline, 6, 12 and 18 months (and 24 months for the first 204 enrollees). This letter will be mailed in the event the participant’s phone number has been identified as either no longer in service, appears disconnected, or is now an incorrect number for the respective participant.

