Health Services Utilization. Physician visits, emergency department visits, hospital admissions, nursing home admissions (distinct from respite care), home care services, and pharmacy data for the period 12 months preceding enrollment and during the 18 months (or 24 months for the first 204 enrollees) of the intervention will be collected from the VISN-22 Data Warehouse. The VISN-22 Data Warehouse contains detailed clinical data about Veterans Administration care (including hospitalizations, clinic visits, prescribed medications and demographics) for 5 hospitals and 28 community-based clinics within the VA Desert Pacific Healthcare Network. The database includes admissions to non-VA hospitals if the VA reimburses those hospitals for the care delivered. CHAPS investigators will prepare a query to the VISN-22 Data Warehouse in Year 4 for these data on study participants.

Missing-data, respondent dropout, interviewer bias.

Missing-data: Data collected from medical record abstraction and administrative records will be complete and will not contain missing data. All survey data is collected by immediate computer entry using a computer software program (Microsoft Infopath or Microsoft Access) that will be programmed to incorporate appropriate skip patterns and flag invalid entries as the RA administers the telephone survey. This computer based data collection will produce a clean dataset with minimal missing data and no out-of-range entries. Periodic data quality checks will be carried out by the data manager to identify systematic patterns of missingness that may occur during data collection.

Respondent dropout: In order to reduce dropout due to the participant being unreachable, we will collect multiple contact phone numbers at enrollment and implement tracking procedures for contact attempts by the study team as outlines in the human subjects section. A toll-free number will be available for participants to reach the research staff and flexible interview times will be offered to participants. If necessary, surveys can be completed over multiple contacts with the participants.

Interviewer bias: Study research assistants that conduct the telephone surveys, and the nurse abstractors who conduct the medical record abstractions will be blinded to the intervention status of participants.

Data Management and Quality Control. Research subject level data will be maintained in 3 separate files:

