Hire nurses to cover GLA, LV, LL, LB & SD	---			#	#				
Train all nurse care managers	---	---	---	#	#				
CHAPS care management activities		---	---	X	---	---	---	---	#
Intervention refinement based on NCM feedback				---	---				
MS Access programming of CHAPS tools	---	---	---	---					
Abstract medical records							X	X	#
Analyze data and prepare manuscripts				---		---			#
Produce annual project reports		---		---		---		---	#
DISSEMINATION ACTIVITIES									
a. Present at VA National PD Consortium mtg			---		---		---		#
b. Present to VISN 22 leadership annually			---		---		---		#
c. Present to Nursing Research Adv Group			X		---		---		#
d. Apply to My HealtheVet Clinical Advisory Board to develop a Condition Center for PD									#
e. CIPRS to cyber seminars			X			---			#
f. Present to community organization leadership			X			---			#
g. Office of Quality Performance (OQP): PD Toolkit									#
h. Prepare proposal to HSR&D for roll out									#
i. Register with clinicaltrials.gov and update	---								#

PROJECT MANAGEMENT SCHEDULE Updated December 2015 NRI 11-126

KEY --- ongoing/scheduled X deleted previously scheduled activity # updated to accommodate project extension through 4/30/2017										
Project Months	Year 1	Year 2		Year 3		Year 4		Year 5		Year 6
	5/1/12-9/30/12	10/1/12-4/30/13	5/1/13-9/30/13	10/1/13-4/30/14	5/1/14-9/30/14	10/1/14-4/30/15	5/1/15-9/30/15	10/1/15-4/30/16	5/1/16-9/30/16	10/1/16-4/3-/17
	FY12	FY13	FY13	FY14	FY14	FY15	FY15	FY16	FY16	FY17
ACTIVITIES	0-6	7-12	13-18	19-24	25-30	32-36	37-42	43-48	49-53	54-60
Annual Advisory Board meeting			X	---		---		---		#
Steering Committee teleconf meetings		---	---	---	---	---	---	---	---	#
Weekly project and teleconf site meetings	---	---	---	---	---	---	---	---	---	#
Project internal DSMB meetings		X	---	---	---	---	---	---	---	#
Weekly mentor-mentee meetings	---	---	---	---	---	---	---	---	---	#
IRB approvals; annual renewal & Vendorizations	---		---		---		---		---	#
Patient identification from VISN 22 Data Warehouse & VHA National Data Systems (NDS)	---			X	---					
Vet patient lists with providers	---	---	---	---	---	---	#			
Recruit and enroll study participants	---	---	---	X	---	---	#	#		
Collect baseline measures	---	---	---	---	---	---	#	#		
Collect 6, 12, & 18-mo follow-up measures		---	---	---	---	---	---	---	---	#
Collect 24-mo follow-ups on first 204 enrollees							---	---	---	#
Hire nurses to cover GLA, LV, LL, LB & SD	---			---	---					

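### The cost offset is declared from the VA perspective, but the only administrative utilization source covers VISN 22, and the plan does not say how VA care in other VISNs is captured

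*Combined protocol and SAP*

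**What the plan says.** Specific Aim #2 sets out to "measure associated costs and cost offsets from the VA perspective, to provide regional and national VA leadership with data" on sustaining and spreading the program. The data-collection paragraph of the Specific Aims puts source and perspective in one phrase: "using data from VISN Data Warehouse, from the VA perspective". The section on advantages of the study design (Research Design and Methods 7) repeats that the cost analysis takes the VA perspective.

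Under Health Services Utilization in Research Design and Methods 6, physician and emergency visits, hospital and nursing home admissions, home care and pharmacy data "will be collected from the VISN-22 Data Warehouse". That warehouse is described as holding VA care "for 5 hospitals and 28 community-based clinics within the VA Desert Pacific Healthcare Network". It also includes VA-reimbursed admissions to non-VA hospitals. The Missing-data paragraph that follows declares administrative records complete.

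Under Specific Aim #2b in Research Design and Methods 7, units of service are multiplied by standard VA unit costs. Some self-reported use from the telephone survey is added to the administrative data. Arms are compared by a two-sample t test and by regression. The one cost sensitivity analysis listed excludes participants who died.

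**The concern.** The declared perspective is wider than the administrative data described. Under a rule of units times unit cost, a unit that no source records adds nothing to the total, so missing care reads as cheap care. Because the records are declared complete, nothing in the plan would flag this.

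Such care is plausible. Background 2 describes "referral and research collaborations across the eight sites in two VISNs", while all five trial sites lie in VISN 22. The survey section notes that "Occasionally Veterans move and/or change their telephone numbers".

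At stake is whether the cost total and the offset answer the question put to national leadership. The same costs decide whether a cost-effectiveness analysis may follow, and they feed the business case described under Dissemination 2.

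**Working it through.** The plan states no figure for this point, so there is nothing to reproduce. The check has two parts.

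**1. Coverage, source by source**

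| VA-financed care | Recorded by the sources named? |
|---|---|
| VA care at VISN 22 hospitals and clinics | Yes, warehouse |
| Non-VA hospital admissions reimbursed by VA | Yes, warehouse |
| Care at VA facilities in other VISNs | Not by the warehouse as described; self-report unspecified |
| VA-paid non-VA care other than admissions | Not stated |

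The plan does not say which services are self-reported, whether VA care outside VISN 22 is among them, or how reports are merged with warehouse records and costed. A mover who cannot be reached by telephone also gives no survey data. Self-report may narrow the gap, but as written it cannot be relied on to close it.

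**2. Size, under assumptions.** The share of care outside VISN 22 is not in the documents. Everything below is illustration and assumes that self-report recovers none of it.

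*Share of cost missed.* Missed share = q × h, where q is the proportion of participants with VA care outside VISN 22 (assumed 0.02-0.10) and h is the proportion of their cost incurred there (assumed 0.3-0.6). Low end: 0.02 × 0.3 = 0.006. High end: 0.10 × 0.6 = 0.06. So 0.6-6% of total VA cost is missed.

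*Effect on the offset.* Observed offset = (1 − s1) × C1 − (1 − s0) × C0, where s1 and s0 are the uncaptured shares of cost in the intervention and usual-care arms. Take assumed true means C0 = 100 and C1 = 90, a true offset of −10.

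| s0 (usual care) | s1 (intervention) | Observed offset |
|---|---|---|
| 2% | 2% | 88.2 − 98 = −9.8 |
| 5% | 5% | 85.5 − 95 = −9.5 |
| 10% | 10% | 81 − 90 = −9.0 |
| 20% | 20% | 72 − 80 = −8.0 |
| 5% | 10% | 81 − 95 = −14.0 |
| 10% | 5% | 85.5 − 90 = −4.5 |

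Equal shares shrink the offset in proportion. Unequal shares move it in either direction.

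*A milder difference between arms.* Suppose q differs by 3-5 percentage points and half of those participants' cost is lost. The shift is 0.03 × 0.5 = 1.5% to 0.05 × 0.5 = 2.5% of mean cost. With equal arms, a pooled share p allows a difference of at most 2p, so a 5-point difference needs p of at least 2.5%.

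*Against sampling error.* With 150 per arm, the standard error of the difference in mean cost is CV × √(2/150) = 0.115 × CV. That is 11.5% of mean cost if the coefficient of variation is 1, and 23% if it is 2 (both assumed). The 1.5-2.5% shift is then 1.5/23 = 0.07 to 2.5/11.5 = 0.22 of one standard error.

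**The case against.** The strongest reply is that the VA perspective says whose costs count and does not promise a national census of care. The Specific Aims name the regional warehouse and the perspective together, eligibility rests on VISN 22 diagnosis codes, and unit costs come from a VA-wide source. This stands in part. It explains the choice, but it does not make a one-VISN extract complete for the VA as payer, and the aim names national leadership as an audience.

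A reader might infer that utilization comes from the warehouse alone and that outside care is set to zero. The documents do not support this. Research Design and Methods 7 adds self-report, and no section sets such care to zero. It goes uncounted only where self-report also misses it.

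A reader might also infer that leakage is documented. It is not. Background 2 mentions referral collaborations without direction or volume, the regional PADRECC center is itself in VISN 22, and the sentence on moving concerns lost telephone contact.

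Randomization is by patient and stratified by site, so under-capture should be similar in the two arms. That stands as the main expectation. It is not a guarantee, because the intervention works through referral and access to specialists and so could change where care is received.

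Finally, National Data Systems appears only in the project schedule, for identifying patients. Nothing says that it holds utilization for these services. That stands, and the fix is conditional on it.

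**Conclusion.** The mismatch is real. Costs are declared from the VA perspective, the administrative source covers one VISN plus VA-reimbursed non-VA admissions, and the completeness statement is unsupported for that perspective. How much cost is missed cannot be known from the documents.

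The most likely effect is a roughly proportional shrinkage of the offset. A difference between arms could bias it either way. Under the milder assumptions above the bias is 1.5-2.5% of mean cost, which is 15-25% of an offset that is itself 10% of mean cost, yet well below one standard error. The larger shifts in the table need a 5-point gap between arms in the share of cost missed, and no section documents a gap of that size. A claim of substantial or directional bias would go beyond the documents.

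Only Aim 2b and what follows from it are touched. The primary outcome and Aim 1 are not. The change is worth making because it is cheap and brings the result into line with its label.

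**What to change.** In the Specific Aims, in Health services utilization (Research Design and Methods 5), in Health Services Utilization (Research Design and Methods 6) and in Specific Aim #2b (Research Design and Methods 7), run the same utilization query, with the same services and time windows, on a national VHA source. The National Data Systems already listed in the schedule are a candidate, once it is confirmed that they supply these services. Use that total as the VA-perspective cost and keep the VISN-22-only total as a secondary, regional view.

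If national data cannot be obtained:
- label the result a VISN 22 cost;
- remove the statement that administrative records will be complete;
- add a sensitivity analysis for participants known to have moved or to have used VA care outside VISN 22.

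The cost is one further data request with some waiting, a short amendment and a little more programming. No new patient contact is needed.
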